1. INTRODUCTION

Obesity is a chronic disease characterized by an excessive body fat accumulation, which has a negative impact on health and affects the physical, social and emotional wellbeing. A double-blind study will be carried out using a weight loss program based on a low-fat, normoprotein, controlled ketogenic diet, followed by a metabolic adaptation process. During the weight loss process, psycho-emotional support and personalized physical activity supervision will be provided in order to modify lifestyle habits along with nutrition. In this study, supervision during 24 months of the weight lost is proposed to ensure the stability of the results obtained. In the initial phase where the diet process is fully controlled, the control group will receive the weight reduction program proposed by the WHO task force.

The weight loss program is developed according to the characteristics of each patient and includes medical control, dietary-nutritional supervision, introduction of a physical activity program and psycho-emotional support.

The primary objective of this study is to test the effectiveness, safety and security of this intervention method for weight loss and compare it with a conventional method for weight loss.

This document includes all the background information for the use of the so-called very low-calorie ketogenic diet, the hypotheses to be tested in this study, the methodology of how the objectives will be demonstrated and the statistical analyses used, the table of variables to be studied, the bibliography consulted and finally the materials used for data collection and management.

2. BACKGROUND.

Obesity is a chronic disease characterized by an excessive accumulation of body fat, which impacts health negatively and affects the physical, social and emotional wellbeing. It is a growing health problem with a high prevalence worldwide and a high impact in Mexico (1). According to a study conducted by the Food and Agriculture Organization of the United Nations (FAO), Mexico has become the country with the highest obesity rate, with 32.8% obese people, above the United States with 31.8% (2), such data definitely underestimates the problem in Mexico, since according to the National Health and Nutrition Survey (ENSANUT) 2018, 42.5% of men over 20 years old are overweight and 30.5%, are obese; while in women these figures correspond to 36.6 and 40.2%, respectively (3).

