The studies carried out to date with diets that are very-low in carbohydrates, high-protein and low in fat have demonstrated their efficacy in reducing weight both in the short and long term (9,10). There is increasing evidence that rapid weight loss, such as that achieved with this type of nutritional intervention, is associated with better long-term results, and initial weight loss has even begun to be considered as a predictor of long-term weight maintenance.(11,12,13,14) Furthermore, in 2012, George Blackburn himself acknowledged in an article that the tendency to use commercial rapid weight loss programs is appropriate, since they achieve better results.(15,16,17.)

The anecdotal experience obtained in daily practice with the Zélé method and products has shown great effectiveness in weight reduction, however, so far there is no scientific evidence of its efficacy or its medium and long term effects. By conducting a double blind study, our objective is to evaluate the efficacy and safety of this nutritional intervention for the reduction and maintenance of weight loss, due to the fact that it is possible, according to Zélé's food engineering system, to build a reduced carbohydrate diet under the same concept of Zélé's products for a controlled ketogenic diet, as well as to perform a 12 and 24 months follow-up of the cohort to assess its efficacy not only in the initial stages, but also during the 24-month follow-up. The aim of this study is also to evaluate patient adherence to treatment, which in most studies reports a dropout rate of over 40% (4). In addition,

the characteristics of weight loss and the preservation of muscle mass and strength and finally patient satisfaction with their treatment will be evaluated.

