7. METHODOLOGY

7.1. Study setting.

The study will be conducted in Mexico City under the sponsorship of Zélé® and in collaboration with the VIME Weight Loss and Wellness Center of Mexico. During the year 2021 and with follow-up for 24 months. An open call will be made through different media including social networks for the recruitment of patients who meet the inclusion criteria and must present themselves for a clinical evaluation in which pathological history, clinical status, heart rate, blood pressure, oxygenation and temperature will be recorded. Nutritional assessment in which anthropometry and multifrequency electrical bioimpedance analysis (MFBIA) will be performed to determine body composition. Patients will have to bring a Complete Blood Count, a biochemical profile that includes the following determinations: Fasting blood glucose, glycosylated hemoglobin, urea, creatinine and uric acid, cholesterol, triglycerides, LDL, HDL and VLDL, direct and indirect bilirubins, alanine and aspartate aminotransferases, gamma-glutamyl transferase and albumin, determination of serum electrolytes sodium, chloride, potassium, magnesium, phosphorus and calcium, Fasting Insulin , HOMA index calculation. In addition to a thyroid function panel and arterial blood gases. They will be instructed during recruitment for the studies to be performed in a clinical laboratory, under the current standardization and with standardized and perfectly calibrated automated equipment, and a request will be made to keep the vials of the patients' plasmas. Patients who meet all the inclusion criteria will be selected and will have an interview with the principal investigator in which they will sign their letter of commitment and informed consent, then they will be subjected to the randomization process with a 2:1 allocation for treatment and controls, respectively. Subsequently, they will be submitted to the two nutritional treatments and will be clinically evaluated every week and will receive nutritional, psycho emotional and physical activity counseling. At each visit, adverse effects, changes in clinical status will be recorded and the presence of ketone bodies in capillary blood will be determined with the Freestyle Abbott optium H β -Ketone (β -hydroxy-Butyric Acid) device; during nutritional counseling, MFBIA will be performed using the In-Body 570 body composition analyzer. When ketone body levels above 0.8 mmol/liter are detected, a new arterial blood gas analysis will be taken; for patients who do not have elevated ketone bodies, an arterial blood gas will be taken between the first and second week of treatment. A new biochemical profile determination will be performed when patients have lost 40% of their overweight or between 10 and 12 kg, whichever

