
occurs first. And new biochemical evaluations when the decrease of Ketone Bodies below 0.4 mmol/l is detected or when patients have reached a loss of 60 to 70% of their overweight and one more when they reach their weight loss goal. Subsequently, only clinical and nutritional follow-up will be given along with psycho-emotional support and physical activity advice every 3 months up to 12 months and every 6 months up to 24 months.

7.2 Study design.

Longitudinal, Prospective, Controlled Randomized Clinical Trial.

7.3 Study population.

Patients of either sex, between 18 and 60 years of age, with a body mass index (BMI) between 30 and 35 kg/m².

7.4 Sample.

The sample will be obtained by open call through social media and all patients who come with their clinical analysis and meet the inclusion criteria will be evaluated until the sample number is reached. In order to obtain 95% power in this Controlled Clinical Trial and with a 95% CI, a 3:1 case-control ratio is established, considering a 35% attrition rate, 56 cases and 32 controls will be included and subsequently crossed to become cases. (Calculated with EPIinfo STATCALC for sample size)

Two blinded arms are proposed for the physician and the patient.

Obese patients assigned to the low-fat normoprotein controlled ketogenic diet group.

Obese patients assigned to a balanced hypocaloric diet. And who will subsequently be subjected to a controlled normoproteic low-fat ketogenic diet.

7.5 Inclusion, exclusion and elimination criteria.

7.5.1 Inclusion:

- Men and Women
- 18 to 60 years of age
- With BMI between 30 and 35 Kg/m²
- Who has not taken weight loss treatment in the last 6 months

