Arterial pH	Indicates the amount of hydrogen ions contained in the blood.	Determines the degree of acidity or alkalinity of the blood.	Quantitative, Ratio minimum 7.35 maximum 7.45	Registration form. Blood analysis
Lactic Acid	Substance produced by muscle tissue and blood cells. Lactic acid levels increase when oxygen levels decrease.	Acidic substance that accumulates in the blood and causes a decrease in pH, its ionized form is lactate.	Quantitative, Ratio 4.5 to 19 mg/l or 0.5 to 2.2 mmol/liter.	Registration form. Blood analysis
Anion Gap	Difference between anions and cations measured in the serum	Difference between anions and cations measured in serum	Quantitative, Ratio unit mEq/l minimum 8 max. 12	Registration form. Blood analysis
Excess Base	the amount of acid required to return the pH of an individual's blood to a normal value	the amount of acid required to return the pH of an individual's blood to a normal value	Quantitative, Ratio Minimum -2 maximum + 2	Registration form. Blood analysis

Satisfaction and Adherence				
Satisfaction Survey	Positive assessment of the different dimensions of the medical care received	Interrogation Very Satisfied to Very Dissatisfied	Categorical Nominal	Registration form.
Adherence to treatment	Taking medication according to the dosage of the prescribed schedule; and persistence, taking medication over time.	Interrogation Complied or did not comply with the program.	Categorical Nominal	Registration form. adherence to treatment

7.7 Data collection.

All data will be captured and recorded digitally in each of the queries through the Google Forms platform to consolidate the information in Google Sheets.

In the consultation, medical history data will be collected in the form of interrogation, weight will be determined through electronic scales, height through calibrated stadiometers, All measurements will be performed according to the WHO Physical Measurement Guide 2014 (www.who.int/surveillance/steps/Part3_Section4) Annex 1. In addition, a capillary determination of glucose and ketones will be performed at each clinical consultation. Once patients are drawn by lot they will be assigned to one of the control centers distributed in Mexico City, they will always have to go to the same control center (VIME). The consultation visits will be weekly for weight control and clinical check-up and every two weeks alternately for physical and psychological counseling.

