7.10.2 Hypocaloric Balanced Diet

Balanced hypocaloric diet (caloric intake 20% below basal metabolic expenditure measured by Multifrequency Bioelectrical Impedance or calculated according to the FAO/WHO/UN formula (FAO/WHO/UNU (1985). Energy and Protein requirements. Technical Report Series No 724, World Health Organization, Geneva). The usual caloric intake of a balanced hypocaloric diet is between 1,200 and 1,400 kcal per day with a macronutrient distribution of 50% carbohydrates, 25% proteins and 25% fats, according to the Diogenes study (17). 27

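### The protocol claims that physician and patient are blinded, but the procedures it describes do not support that claim

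*Combined protocol and SAP*

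**What the plan says.** Blinding is claimed in three places. Section 1 (Introduction) says "A double-blind study will be carried out using a weight loss program". Section 2 (Background) repeats it: "By conducting a double blind study, our objective is to evaluate the efficacy and safety of this nutritional intervention". Section 7.4 (Sample) names who is blinded: "Two blinded arms are proposed for the physician and the patient". Section 7.2 (Study design) lists the design features and does not mention blinding.

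The only hint of a mechanism is in section 2, which says the sponsor's food engineering makes it possible "to build a reduced carbohydrate diet under the same concept of Zélé's products for a controlled ketogenic diet".

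On procedures, section 7.7 says "a capillary determination of glucose and ketones will be performed at each clinical consultation", and consultations are weekly. Section 7.1 ties action to the result: "When ketone body levels above 0.8 mmol/liter are detected, a new arterial blood gas analysis will be taken". It also orders new biochemistry when ketones fall below 0.4 mmol/l.

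On the diets, section 7.10.1 gives the ketogenic arm staged commercial preparations with vitamin and trace element supplements. Section 7.10.2 gives the control arm a balanced diet, usually "between 1,200 and 1,400 kcal per day", and describes neither preparations nor supplements. Section 1 describes the control treatment as a WHO task force programme.

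**The concern.** A double-blind label tells ethics reviewers and readers that judgement-based outcomes are protected from knowledge of the arm. Several stated objectives in section 5.2 depend on such judgement: satisfaction, adherence, tolerability, and dropout with its causes. Section 7.5.3 also lets the investigator or the sponsor withdraw a patient on their own judgement, and the sponsor's own programme is under test. If staff can tell the arm, these outcomes would be published with a protection they did not have. Discretionary withdrawal could also affect who remains in the weight comparison.

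**Working it through.** The plan gives no figure for blinding: no expected ketone values by arm and no planned test of blinding. There is nothing to reproduce, so the check sets the claim against the procedures.

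**1. The physician.**
- Ketones are measured in both arms at each weekly visit (sections 7.1 and 7.7).
- Values above 0.8 mmol/l or falling below 0.4 mmol/l trigger tests (section 7.1), so someone in clinical care must see them.
- Section 2 gives the programme's physician the task of controlling side effects of ketosis.
- Section 2 puts the onset of ketone formation at 48-72 hours, before a first weekly visit at about day 7. That sentence describes a diet with carbohydrate cut to a minimum, not the study diet itself, so the timing is indicative.
- No masked reading, blinded assessor, code-break procedure or separation of dietary from assessing staff is described.

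**2. The patient, initial phase** (sections 7.10.1 and 7.10.2).

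| Feature | Ketogenic arm, frank ketosis | Control arm |
|---|---|---|
| Form | commercial preparations plus vegetables, 5 meal times | balanced diet, no preparations described |
| Energy | 650-730 kcal/day | usually 1,200-1,400 kcal/day |
| Carbohydrate | under 60 g/day | 50% of energy |
| Supplements | vitamins and trace elements | none described |

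- Energy gap: 1,200 − 730 = 470 to 1,400 − 650 = 750 kcal/day.
- Energy ratio: 650/1,400 = 46% to 730/1,200 = 61%.
- Control carbohydrate, assuming 4 kcal/g (not in the documents): 0.5 × 1,200/4 = 150 g to 0.5 × 1,400/4 = 175 g per day. Against the 60 g ceiling this is at least 150/60 = 2.5 times as much.

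**3. How long the contrast lasts.** Mixed ketosis adds 100-150 kcal/day, giving 650 + 100 = 750 to 730 + 150 = 880 kcal/day. The gap is then 1,200 − 880 = 320 to 1,400 − 750 = 650 kcal/day. The transition stage is 1,300-1,500 kcal/day. The integral and maintenance phase has the same 50/25/25 split of macronutrients as control. The contrast therefore belongs to the ketogenic stages.

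**4. Can the unblinding be sized?** Let *s* be the share of ketogenic patients, and *c* the share of controls, reading above 0.8 mmol/l. With 56 and 32 patients, one reading identifies the arm correctly with probability (56/88)·*s* + (32/88)·(1 − *c*). Always guessing the larger arm is right 56/88 = 64% of the time. All values of *s* and *c* below are assumptions.

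| *s* | *c* | Correct |
|---|---|---|
| 95% | 5% | 0.636 × 0.95 + 0.364 × 0.95 = 95% |
| 90% | 5% | 0.636 × 0.90 + 0.364 × 0.95 = 92% |
| 70% | 10% | 0.636 × 0.70 + 0.364 × 0.90 = 77% |
| 60% | 20% | 0.636 × 0.60 + 0.364 × 0.80 = 67% |

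The result runs from barely above guessing to near certainty, so no single figure can be defended. Repeated weekly readings would add information, which this calculation leaves out.

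**5. Room for an effect on who is analysed.** Section 7.4 allows for 35% attrition: 0.35 × 88 = 30.8, about 31 patients. The documents do not say how many of these would be discretionary withdrawals.

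**The case against.** The best defence is the section 2 sentence on a product-matched diet, which is offered as the reason a double-blind design is feasible. It is only a statement of possibility. Section 7.10.2 provides no such product, and a look-alike would not hide ketone readings from the physician.

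Four other objections stand and limit the point:

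- **The blood gas does not reveal the arm.** A reader might infer that it does from the 0.8 mmol/l trigger. Section 7.1 also orders a gas in the first or second week for patients without raised ketones. The ketone value is the marker.
- **Patient unblinding is not certain.** The text available does not show whether patients learn their ketone values or what the other arm receives. A patient who knows only one diet may not be able to name the arm.
- **The later crossover adds little.** Controls move to the ketogenic diet after the control period, and nothing shows that this unblinds the earlier comparison.
- **The main hypotheses are less exposed.** H1 and H3-H5 rest largely on scale weight, laboratory values and bioimpedance.

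**Conclusion.** The blinding claim is not supported by the described procedures. The case is strongest for the physician: an unmasked ketone result that drives action is available at every weekly visit. For the patient, blinding is unsupported because the diets as written differ in form, energy, carbohydrate and supplements, and no matched product is specified.

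A reader might go further and infer that nobody could stay blind, or that the arm is known in over 90% of patients. The documents do not support either. No ketone distribution by arm is given, and assumed rates move the single-reading figure from 67% to 95%. Nor do they support reading the 46-61% energy ratio as a contrast for the whole trial; it applies to frank ketosis and to the usual control intake.

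The exposure is greatest for satisfaction, self-reported adherence, tolerability and discretionary withdrawal. It is smaller for scale weight and laboratory values. The conclusion rests on the absence of any masking procedure in the text and needs no assumption about ketone rates.

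**What to change.** - Describe the trial as open-label in sections 1 and 2, and remove the blinding statement from section 7.4.
- Give the analyst coded arms.
- Report satisfaction, adherence, tolerability and discretionary withdrawals by arm, labelled as unblinded outcomes.
- Do not describe the nutritionists' bioimpedance readings as blinded. Section 7.1 places them within nutritional counselling, so those staff know the diet whether or not they see ketone results. Blinded measurement would need someone outside dietary care.
- If the sponsor wants to keep any blinding claim, reconcile sections 1, 2 and 7.4 with section 7.10.2 and the visit procedures in sections 7.1 and 7.7, so that the protocol states how blinding is achieved.

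The first four changes cost protocol wording and a coded data file, and need no extra staff. The downside is a less favourable design label. Keeping a blinding claim would cost more; the amount depends on the mechanism chosen.

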7.5.2 Exclusion

- Pregnant or breastfeeding patients.
- Patients with severe eating disorders, alcoholism, or drug addiction.
- Patients with severe psychological disorders (e.g. schizophrenia, bipolar disorder).
- Patients with hepatic alteration defined as increase of ALT, AST, GGT more than 4 times the reference value.
- Patients with renal impairment defined as a glomerular filtration rate below 60 ml/min.
- Patients with type 1 or insulin-dependent DM, or DM2 on insulin therapy.
- Patients with obesity caused by endocrinological diseases (except type 2 DM).
- Patients with hemopathies.
- Cancer patients.
- Patients with active cardiovascular or cerebrovascular disease (heart rhythm disorders, recent infarction [<6m], unstable angina, decompensated heart failure, recent vascular accident [<6m]).
- Patients with gout.
- Patients with renal lithiasis.
- Patients with cholelithiasis.
- Patients with depression.
- Patients with electrolyte disorders.

- Patients with orthostatic hypotension.
- Patients with an altered or abnormal electrocardiogram.

7.5.3 Elimination criteria

- Patients who drop out and decide to stop participating in the study.

(The patient has the right to withdraw from the study at any time, without the need to offer any explanation and without affecting the patient's future care or health care).

- The patient may also be withdrawn from the study at any time at the discretion of the investigator or the sponsor, for administrative or behavioral reasons or for missing two consecutive follow-up visits.
- Patients who during follow-up present any of the following criteria: Any serious adverse event
- Incoercible vomiting and nausea that do not allow following an oral diet.
- Worsening of diabetes control in patients with type II diabetes mellitus or insulin resistance
- Uncontrolled hypertension (SBP > 150 mmHg or SBP < 90 mmHg in successive repetitions).
- The reasons for abandonment of the study must be clearly documented in the registration notes. Any adverse reactions will be immediately reported to the Pharmaco-Surveillance system in charge of [name] [name] Principal Investigator.

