5. OBJECTIVES

5.1 *General Objective*

To evaluate differences in the response of weight, body composition and metabolic biochemical parameters among obese patients following a normoprotein low-fat controlled ketogenic diet compared to a balanced BIEM).

5.2 *Specific Objectives*

- Intra- and intergroup comparison of patient weight and BMI reduction between baseline and subsequent follow-up monitoring visits.
- To determine the percentage of patients with weight loss equal to or greater than 10% of initial weight and the time it took for patients to reach this figure.
- Evaluate the evolution of comorbidities associated with obesity (HT, hyperglycemia or diabetes, hypercholesterolemia, hypertriglyceridemia, apneas), control of clinical and analytical parameters and changes in medication during the weight loss process and during follow-up.
- To know the tolerability of the diet: Incidence of side effects during the development of the study,
- Safety of the intervention diet: appearance of analytical alterations, especially of the ionic profile, renal function and hepatic function, incidence of serious adverse events.
- Assess diet adherence and dropout rate and cause.
- To know patient satisfaction with the assigned nutritional program.

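### Patients are eliminated for events that overlap with the trial's own outcomes, and the plan provides neither for outcome collection after elimination nor for analysis as randomised

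*Combined protocol and SAP*

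**What the plan says.** Section 7.5.3 lists the grounds for elimination. Apart from voluntary dropout and discretionary withdrawal, four are events during follow-up:

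- Safety, where the list opens: "Patients who during follow-up present any of the following criteria: Any serious adverse event"
- Blood pressure, the last event named: "Uncontrolled hypertension (SBP > 150 mmHg or SBP < 90 mmHg in successive repetitions"
- Glycaemia, restricted to a subgroup: "Worsening of diabetes control in patients with type II diabetes mellitus or insulin resistance"
- Tolerability of the diet: "Incoercible vomiting and nausea that do not allow following an oral diet"

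For patients who leave, the section requires that "The reasons for abandonment of the study must be clearly documented in the registration notes" and that adverse reactions be reported. It says nothing about later measurements.

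Section 5.2 sets several objectives that bear on this. One concerns response: "To determine the percentage of patients with weight loss equal to or greater than 10% of initial weight". Another concerns comorbidity: "Evaluate the evolution of comorbidities associated with obesity (HT, hyperglycemia or diabetes, hypercholesterolemia, hypertriglyceridemia, apneas". On tolerability it asks how often side effects occur, and on safety it includes the "incidence of serious adverse events". In section 6, H2 concerns safety and H3 the regulation of metabolic syndrome.

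Sections 7.1 and 7.7 plan weekly clinical visits with adverse effects recorded, body composition by bioimpedance, and capillary glucose and ketones at each consultation. Clinical follow-up then runs every 3 months to month 12 and every 6 months to month 24. Laboratory profiles are tied to weight and ketone milestones, not to fixed dates.

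Section 7.9 names t-tests, chi-square, one-way ANOVA and repeated-measures ANOVA, within and between groups. It gives no analysis set and no rule for missing data. Section 7.4 mentions loss only as 35% attrition in the sample size, and says that controls later cross to the ketogenic diet without saying when.

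**The concern.** Whether a patient is still under observation at a late visit depends partly on how that patient has fared since randomisation. Patients whose glycaemic control deteriorates, who have a serious event, or who cannot tolerate the diet are the ones whose later values are not provided for. Comparing those who remain compares groups filtered by outcome, and randomisation no longer guarantees that the groups are alike.

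Two kinds of result are exposed. Within-arm change and final-visit means, which the plan intends to report, are affected even if both arms lose patients equally. Between-arm differences are affected if elimination differs by arm. That is possible, because section 7.10 sets 650 to 730 kcal/day in frank ketosis against a usual 1,200 to 1,400 kcal/day for the balanced diet.

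The percentage losing at least 10% of weight, and the incidence of each event, also have no stated denominator. The same data could give different percentages depending on whether eliminated patients are counted, and that choice could be made after the results are known.

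**Working it through.** **Step 1. Match each trigger to an outcome.**

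| Trigger (7.5.3) | Outcome it overlaps with |
|---|---|
| Serious adverse event | Serious event incidence (5.2); H2 |
| Intractable vomiting and nausea | Incidence of side effects (5.2); H2 |
| Deteriorating diabetes control | Evolution of hyperglycaemia or diabetes (5.2); H3 |
| Repeated SBP above 150 or below 90 | Evolution of hypertension (5.2); H3 |

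**Step 2. Look for protection elsewhere.** Sections 7.1 and 7.7 describe visits for study patients and do not mention eliminated ones. The background speaks of following the cohort to 12 and 24 months, also without mentioning them. No section mentions intention to treat, another analysis set, or missing-data handling. The 35% attrition in 7.4 leaves about 56 × 0.65 = 36 and 32 × 0.65 = 21 patients. That allowance concerns numbers, not selection.

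**Step 3. Separate what is kept from what is lost.** Kept: the triggering event, the reason for leaving, and weight and capillary glucose up to elimination. Not provided for: later weight, body composition, blood pressure and clinical values.

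**Step 4. Scale, by illustration only.** The plan has no figure of its own to reproduce here. It gives no SD, no definition of worsening control, and no number of patients subject to each trigger. Everything in this step is therefore assumed.

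Let X be the glycaemic change that triggers elimination and Y a later change. Both are standard normal with correlation r, and higher is worse. A share p with the highest X is eliminated, and Y is then missing. With z the (1 − p) quantile and φ the normal density:

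mean Y of those remaining = −r × φ(z) / (1 − p).

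For p = 0.10, z = 1.2816 and φ(z) = 0.1755. With r = 0.5, the mean is −0.5 × 0.1755 / 0.90 = −0.0975, or about 0.10 SD too favourable.

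| p | r = 0.3 | r = 0.5 | r = 0.7 |
|---|---|---|---|
| 0.05 | −0.033 | −0.054 | −0.076 |
| 0.10 | −0.058 | −0.097 | −0.136 |
| 0.20 | −0.105 | −0.175 | −0.245 |

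Over a whole arm in which a share q is subject to the trigger, and m is the shift above:

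q(1 − p)m / [q(1 − p) + 1 − q].

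With p = 0.10 and r = 0.5:

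- q = 0.2: 0.18 × (−0.0975) / 0.98 = −0.018.
- q = 0.5: 0.45 × (−0.0975) / 0.95 = −0.046.

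The extremes are −0.006 (p = 0.05, r = 0.3, q = 0.2) and −0.109 (p = 0.20, r = 0.7, q = 0.5).

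A simulation of 2,000,000 draws per pair of p and r agreed with the formula. An estimate that also used the triggering value was within 0.002 of zero. That follows by construction, because elimination in this model depends only on the observed X.

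**Step 5. Why no figure is given for blood pressure.** The rule needs successive readings and the documents give neither their number nor an SD. It also acts at both ends, so even the direction depends on the blood-pressure distribution.

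**The case against.** Almost every safety withdrawal rule is triggered by a safety outcome, so the overlap alone proves nothing. That is right. The fault is the silence on follow-up and analysis, and the missing analysis set affects voluntary dropouts too. It matters most here because these losses are tied to outcome by rule.

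Four stronger readings are tempting, and the documents do not support them.

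- **That serious events disappear from the safety count.** They do not. Adverse effects are recorded at each visit and reported, so the events can be counted. Only the denominator and the later follow-up are undefined.
- **That eliminated patients' data are deleted, or that they are excluded from analysis.** The text says neither. The analysis set is simply unspecified.
- **That later measurement is forbidden.** Section 7.5.3 speaks of withdrawal from and abandonment of the study, which suggests that visits stop. It does not bar further collection; it does not provide for it.
- **That the comparison is biased towards the ketogenic diet.** If elimination is alike in both arms, between-arm bias is about nil. If it differs, the direction depends on which arm loses more patients and which ones.

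It is also fair to say that the illustrated effect is small over an arm unless elimination is frequent. And because laboratory profiles follow milestones, no fixed late laboratory value exists to which the illustration would strictly apply. Both points stand. They limit the claim about size, not the gap in the plan.

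Separately, the blood-pressure line is labelled as hypertension but includes a low limit. The authors should reconcile the two; no view is taken here on which is intended.

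**Conclusion.** The point holds as a gap in design and analysis and should be fixed. By rule, patients leave for events that overlap with the trial's outcomes. Nothing provides for their later values, and the named tests by default leave out patients who lack the needed values. Within-arm and final-visit results are selected on outcome. Between-arm results may be biased if elimination differs by arm.

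Size and direction cannot be derived from the documents. The only figure offered is an illustration for glycaemia: about 0.10 SD too favourable (0.03 to 0.24) among patients subject to the trigger. Over an arm with 20% to 50% subject to it, this is about 0.02 to 0.05 SD (0.006 to 0.11). It rests on assumed normality, 10% elimination (5% to 20%) and correlation 0.5 (0.3 to 0.7). No bias in mean weight loss (H1) has been quantified. The case rests on the missing rules and denominators, not on these magnitudes. Confidence is medium.

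**What to change.** Leave the clinical criteria unchanged.

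**Section 7.5.3.** State that meeting an event-based criterion does not end outcome collection. With the patient's consent, the already planned weight, body-composition and clinical visits continue.

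**Section 7.9.**

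- State the time at which controls cross over. Without it, the randomised comparison has no defined end.
- For the period before that time, analyse all randomised patients in the assigned arm with a method that keeps patients with incomplete data, for example a mixed model for repeated measures.
- Use all randomised patients as the denominator for the 10% weight-loss objective and for each listed event.
- Add a sensitivity analysis that counts eliminated patients as non-responders unless they had already reached 10%. The mixed model assumes data missing at random, which may fail for weight after a serious event or intractable vomiting.

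**Cost.** One statement in 7.5.3, one paragraph in 7.9, and a few more visits for patients already enrolled. Some will decline, so some data will still be missing, and the efficacy figures may be slightly less favourable.
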